2.1 Objectives & Hypotheses	
2.1 Study Objectives
 
Objective 1. (Hypotheses 1 and 2) To assess the acute (1-week) efficacy of adjunctive (added to existing treatments) suvorexant in patients with bipolar disorder and insomnia despite treatment with traditional hypnotic agents, anxiolytics, atypical antipsychotics, mood stabilizers, and/or antidepressants.
 
Objective 2. (Hypotheses 3 and 4) To assess the subchronic (3-month) efficacy of open adjunctive (added to existing treatments) suvorexant in patients with bipolar disorder and insomnia despite treatment with traditional hypnotic agents, anxiolytics, atypical antipsychotics, mood stabilizers, and/or antidepressants
 
2.1.1 Clinical Hypotheses.
 
 1. Primary acute efficacy hypothesis – Adjunctive suvorexant 20 mg at bedtime compared to adjunctive placebo for 1 week in patients with insomnia related to bipolar disorder (307.42), despite receiving treatment as usual will yield significantly greater increases in subjective total sleep time (sTST), as assessed by self-report. 2. Secondary acute efficacy hypothesis 1 – Adjunctive suvorexant 20 mg at bedtime compared to adjunctive placebo for 1 week in patients with insomnia related to bipolar disorder (307.42), despite receiving treatment as usual will yield significantly greater increases in objective total sleep time (oTST), as assessed by sleep actigraphy. 3. Secondary subchronic efficacy hypothesis 2 – Adjunctive open suvorexant 20 mg at bedtime for 3 months in patients with insomnia related to bipolar disorder (307.42), despite receiving treatment as usual will yield significant increases in subjective total sleep time (sTST), as assessed by self-report. 4. Secondary subchronic efficacy hypothesis 3 – Adjunctive open suvorexant 20 mg at bedtime for 3 months in patients with insomnia related to bipolar disorder (307.42), despite receiving treatment as usual will yield significant increases in objective total sleep time (oTST), as assessed by sleep actigraphy.
2.2 Background & Rationale, Significance of Selected Topic & Preliminary Data	
Insomnia is common in patients with bipolar disorder, not only when hypo/manic, but also when depressed, or even euthymic,^{1, 2} and commonly persists despite treatment. Sleep disturbance in remitted bipolar disorder patients may represent a prodrome of an impending mood episode, whereas improvement in sleep quality during an acute mood episode may be an early marker of recovery from the episode.¹ Insomnia therefore represents an important target of treatment in bipolar disorder, regardless of current mood state.¹
 
Preliminary data from our clinic have been largely consistent with previous literature. Thus, among 89 bipolar disorder patients who achieved recovery from a mood episode and were subsequently followed longitudinally in the Stanford Bipolar Disorders Clinic for at least one year, worse daytime dysfunction, subjective sleep quality, sleep latency, and global sleep disturbance on the Pittsburgh Sleep Quality Index (PSQI)³ were associated with the presence of subsyndromal mood symptoms.⁴ In addition, worse PSQI daytime dysfunction significantly predicted a shorter time to mood episode recurrence.⁴
 
Unfortunately, insomnia associated with bipolar disorder can be challenging to treat. Among 69 Stanford Bipolar Disorders Clinic patients who were already taking at

	
least one scheduled (i.e. non-PRN) prescription sedative-hypnotic agent at the time of initial assessment, 55.0% (N=38) complained of insomnia on at least one day within the prior week (unpublished data). Thus, treatment-resistant insomnia is both highly prevalent and associated with poorer longitudinal outcomes in bipolar disorder. More effective treatments for insomnia associated with bipolar disorder are urgently needed.
 
Suvorexant is a novel hypnotic agent that promotes sleep via orexin receptor antagonism.⁵ A phase 3 randomized, double-blind, placebo-controlled study has demonstrated the efficacy and safety of suvorexant, in doses of 10mg to 20mg at bedtime, for the treatment of insomnia in healthy adults.⁶ We propose conducting a randomized, double-blind, placebo-controlled study assessing the efficacy of adjunctive (added to existing treatments) suvorexant in depressed or euthymic (but not hypo/manic) patients with bipolar disorder (Type I, Type II, or Type Not Otherwise Specified) and insomnia despite treatment with traditional hypnotic agents, anxiolytics, atypical antipsychotics, mood stabilizers, and/or antidepressants.


2.3 Study Design
	
Patients with bipolar disorder (Type I, Type II, or Type Not Otherwise Specified) who are currently euthymic or have current syndromal or subsyndromal depressive (but not hypo/manic) symptoms (i.e. have Young Mania Rating Scale [YMRS]⁷ total score < 12), and with insomnia related to bipolar disorder (307.42), with subjective total sleep time (sTST) < 6 hours on at least 1 night during the prior week, will be randomized to receive either adjunctive double-blind placebo or adjunctive double-blind suvorexant 10 mg at bedtime for 3 nights, which as necessary and tolerated then may be increased to 20 mg at bedtime for 4 nights. In all patients, there will be an attempt to increase Suvorexant/Placebo dose from 10 to 20 mg at bedtime after three nights (although Suvorexant/Placebo dose may remain at 10 mg if the patient prefers to do so, though this is expected to be uncommon). Following the 1-week randomized controlled phase, all patients will receive open suvorexant 10 mg at bedtime for 3 nights, which as necessary and tolerated then may be increased to 20 mg at bedtime for 3 months. All patients (i.e. those in both the active drug and placebo group) will revert back to the 10mg dose at the start of the open treatment phase in order to protect the blind.
 
Inclusion Criteria:
 
 1. Adult outpatients (age 18 years and older) meeting Diagnostic and Statistical Manual of Mental Disorders, Fourth Edition, Text Revision (DSM-IV-TR)⁸ criteria for bipolar I disorder (296.70), bipolar II disorder (296.89), or bipolar disorder not otherwise specified (296.80), with concurrent insomnia related to bipolar disorder (307.42). 2. Currently taking ≥ 1 prescription psychotropic medication (hypnotic agents, anxiolytics, atypical antipsychotics, mood stabilizers, and/or antidepressants) for management of bipolar disorder. 3. Subjective total sleep time (sTST) < 6 hours on ≥ 1 night during the prior week, assessed at baseline visit using the Systematic Treatment Enhancement Program for Bipolar Disorder (STEP-BD) Clinical Monitoring Form (CMF).⁹ 
Exclusion Criteria:
 
 1. Current hypo/manic symptoms, as evidenced by YMRS total score ≥ 12, assessed at baseline visit. 2. Current (past 6 months) alcohol or substance use disorder, as determined by assessment with the Mini-International Neuropsychiatric Interview (MINI)¹⁰ at baseline visit. 3. Current psychosis, as determined by assessment with the MINI at baseline visit.

	
4. Women who are currently pregnant or breastfeeding.
 
5. Clinically significant abnormalities on baseline laboratory tests (comprehensive metabolic panel, fasting lipid panel, CBC with differential, thyroid stimulating hormone).
 
6. Presence of any unstable and/or potentially confounding neurological and/or medical disorder.
																																																																																																									
2.4 Study Flow	
  
 	Baseline	Week 0	Week 1	Month 1	Month 2	Month 3	
   
 ADE	X						
 
 MINI	X						
 
 DSM-IV-TR 307.42 checklist	X						
 
 CMF	X	X	X	X	X	X	
 
 YMRS	X	X	X	X	X	X	
 
 MADRS	X	X	X	X	X	X	
 
 sTST	X	X	X	X	X	X	
 
 oTST		X	X	X	X	X	
 
 FISER/GRSEB			X	X	X	X	
 
 CMP	X						
 
 FLP	X						
 
 CBC	X						
 
 TSH	X						
 
 Upreg	X						
  
 
ADE = Systematic Treatment Enhancement Program for Bipolar Disorder (STEP-BD) Affective Disorders Evaluation¹¹; MINI = Mini-International Neuropsychiatric Interview¹⁰; DSM-IV-TR 307.42 checklist = Diagnostic and Statistical Manual of Mental Disorders, Fourth Edition, Text Revision⁸ criteria for insomnia related to bipolar disorder (307.42); CMF = STEP-BD Clinical Monitoring Form⁹; YMRS = Young Mania Rating Scale⁷; MADRS = Montgomery-Asberg Depression Rating Scale¹²; sTST = subjective Total Sleep Time (assessed with STEP-BD CMF at baseline visit, and with electronic self-report sleep diary at subsequent visits); oTST = objective Total Sleep Time (assessed with Actigraph device); FISER/GRSEB = Frequency and Intensity of Side Effects Ratings/Global Rating of Side Effects Burden¹³; CMP = comprehensive metabolic panel; FLP = fasting lipid panel; CBC = complete blood count with differential; TSH = thyroid stimulating hormone; Upreg = Urine pregnancy test (only for women of reproductive potential).
		Baseline	Week 0	Week 1	Month 1	Month 2	Month 3	ADE	X						MINI	X						DSM-IV-TR 307.42 checklist	X						CMF	X	X	X	X	X	X	YMRS	X	X	X	X	X	X	MADRS	X	X	X	X	X	X	sTST	X	X	X	X	X	X	oTST		X	X	X	X	X	FISER/GRSEB			X	X	X	X	CMP	X						FLP	X						CBC	X						TSH	X						Upreg	X					
	Baseline	Week 0	Week 1	Month 1	Month 2	Month 3																																																																																																				
ADE	X																																																																																																									
MINI	X																																																																																																									
DSM-IV-TR 307.42 checklist	X																																																																																																									
CMF	X	X	X	X	X	X																																																																																																				
YMRS	X	X	X	X	X	X																																																																																																				
MADRS	X	X	X	X	X	X																																																																																																				
sTST	X	X	X	X	X	X																																																																																																				
oTST		X	X	X	X	X																																																																																																				
FISER/GRSEB			X	X	X	X																																																																																																				
CMP	X																																																																																																									
FLP	X																																																																																																									
CBC	X																																																																																																									
TSH	X																																																																																																									
Upreg	X																																																																																																									
2.5 Study Procedures	
Patients will have the following assessments:
 
1. Baseline (1 week prior to randomization)
 
Due to COVID-19 restrictions, all assessments will be done remotely via Zoom with clinician and study coordinator. Only the lab tests will be done in person. Medication and Actigraph will be mailed out to participant
 
Diagnostic assessments
 
 • Systematic Treatment Enhancement Program for Bipolar Disorder (STEP-BD) Affective Disorders Evaluation (ADE)¹¹ • MINI • DSM-IV-TR insomnia related to bipolar disorder (307.42) checklist 
Clinical symptom assessments
 
 • STEP-BD CMF, including subjective Total Sleep Time (sTST) • YMRS • Montgomery-Asberg Depression Rating Scale (MADRS)¹² 																																																																																																									

	
Laboratory tests
 
 • Comprehensive metabolic panel • Fasting lipid panel • Complete blood count with differential • Thyroid stimulating hormone • Urine pregnancy test (only for women of reproductive potential) 
2. Controlled Week-0 (Randomization; prior to one week of double-blind, placebo-controlled adjunctive suvorexant) Due to COVID-19 restrictions, all assessments will be done remotely via Zoom with clinician and study coordinator. Medication and Actigraph will be mailed out to participant
 
Clinical symptom assessments
 
 • STEP-BD CMF • YMRS • MADRS • Electronic self-report sleep diary, including subjective Total Sleep Time (sTST) • Sleep actigraphy, including objective Total Sleep Time (oTST) assessed with Actigraph device • Frequency and Intensity of Side Effects Ratings/Global Rating of Side Effects Burden (FISER/GRSEB)¹³ 
3. Controlled Week-1 (after one week of double-blind, placebo-controlled adjunctive suvorexant) Due to COVID-19 restrictions, all assessments will be done remotely via Zoom with clinician and study coordinator. Medication and Actigraph will be mailed out to participant
 
Clinical symptom assessments
 
 • STEP-BD CMF • YMRS • MADRS • Electronic self-report sleep diary, including subjective Total Sleep Time (sTST) • Sleep actigraphy, including objective Total Sleep Time (oTST) assessed with Actigraph device • FISER/GRSEB 
4. Open Month-1 (after one month of open suvorexant) Due to COVID-19 restrictions, all assessments will be done remotely via Zoom with clinician and study coordinator. Medication and Actigraph will be mailed out to participant
 
Clinical symptom assessments
 
 • STEP-BD CMF • YMRS • MADRS • Electronic self-report sleep diary, including subjective Total Sleep Time (sTST) • Sleep actigraphy, including objective Total Sleep Time (oTST) assessed with Actigraph device • FISER/GRSEB
--	---

	
5. Open Month-2 (after two months of open suvorexant) Due to COVID-19 restrictions, all assessments will be done remotely via Zoom with clinician and study coordinator. Medication and Actigraph will be mailed out to participant
 
Clinical symptom assessments
 
 • STEP-BD CMF • YMRS • MADRS • Electronic self-report sleep diary, including subjective Total Sleep Time (sTST) • Sleep actigraphy, including objective Total Sleep Time (oTST) assessed with Actigraph device • FISER/GRSEB 
6. Open Month-3 (after three months of open suvorexant) Due to COVID-19 restrictions, all assessments will be done remotely via Zoom with clinician and study coordinator. Medication and Actigraph will be mailed back to study team using prepaid shipping label.
 
Clinical symptom assessments
 
 • STEP-BD CMF • YMRS • MADRS • Electronic self-report sleep diary, including subjective Total Sleep Time (sTST) • Sleep actigraphy, including objective Total Sleep Time (oTST) assessed with Actigraph device • FISER/GRSEB
2.6 Study Duration	Estimated length of time required to recruit patients and complete the study is 6 years, from September 1, 2015 to August 31, 2021.
2.7 Statistical Analysis and Sample Size Justification	
The investigator will analyze the study data. The blind will be maintained using blinded medication and matching placebo provided by the sponsor. For the final analysis, the clinical database will not be unblinded until medical/scientific review has been completed, protocol violators have been identified (if appropriate), and data has been declared complete. Data will then be unblinded, data analysis will be completed, and the manuscripts will be prepared for publication.
 
Variables/Time Points of Interest
 
Primary outcome – subjective total sleep time (sTST), according to self-report, assessed at Controlled Week-0, Controlled Week-1, Open month-1, Open month-2, and Open month-3.
 
Secondary outcome – objective total sleep time (oTST), according to Actigraph, assessed at Controlled Week-0, Controlled Week-1, Open month-1, Open month-2, and Open month-3.
 
Statistical Methods
 
For the randomized controlled phase, the primary outcome (change in sTST from Controlled Week-0 to Controlled Week-1) for adjunctive suvorexant versus adjunctive placebo will be assessed using a Mixed-Effect Model Repeated Measure (MMRM), with a significance threshold of $p < 0.05$.

	
For this 1-week, double-blind, placebo-controlled trial, assuming a two-tailed alpha of .05, a sample of 50 patients (25 patients taking double-blind adjunctive suvorexant, and 25 patients taking adjunctive placebo) would be required to detect an adjunctive suvorexant treatment effect (compared to adjunctive placebo) of 0.70, with a power of approximately .80, as described in greater detail below.
 
For the open extension study, the key efficacy outcome will be change in sTST from Controlled Week-0 to Open Month-3, stratified by acute treatment arm (i.e., blind adjunctive suvorexant followed by open adjunctive suvorexant, and blind adjunctive placebo followed by open adjunctive suvorexant), using a paired Mixed-Effect Model Repeated Measure (MMRM) analysis, with a significance threshold of $p < 0.05$.
 
Additional secondary analyses include evaluation of change in oTST from Controlled Week-0 to Controlled Week-1 for adjunctive suvorexant versus adjunctive placebo, using MMRM with a significance threshold of $p < 0.05$; and change in oTST from Controlled Week-0 to Open Month-3, stratified by acute treatment arm (i.e., blind adjunctive suvorexant followed by open adjunctive suvorexant, and blind adjunctive placebo followed by open adjunctive suvorexant), using a paired MMRM analysis, with a significance threshold of $p < 0.05$.
 
There are no adjustments for dropout, as we expect no more than 5% dropout by the end of week 1.
 
Multiplicity
 
No correction for multiple comparisons will be used.
 
Power/Sample Size:
 
Based on pooled results in Table 1 of Herring, et al.,¹⁴ we expect baseline mean (SD) sTST in minutes of 317 (64). We expect a robust sTST benefit with suvorexant (60 min increase) compared to placebo (15 minute increase) - admittedly this is a more marked suvorexant-placebo difference (60-15 = 45 minutes, which yields an effect size of 0.70) than in Herring et al. Supplemental Table S1,¹⁴ which had a pooled suvorexant-placebo difference of 33-15 = 18 minutes, which yielded a pooled effect size of only 0.28.
 
Thus, for the primary outcome of the randomized controlled phase, based upon a sample size of n=25 patients per group, and a two-tailed alpha of 0.05, this study has 80% power to detect an effect difference in change in sTST for suvorexant versus placebo of 0.70.

2.8 Specific Drug Supply Requirements	
Suvorexant 10 mg tablets, 20mg tablets, and matching placebo will be supplied by Merck.
 
Drug Supply Requirements:
 
Drug Name: Suvorexant 10 mg tablets. Amount: 3 tabs for days 1-3 of 1-week, randomized, controlled treatment phase (a total of 150 tabs for 50 double-blind suvorexant patients), then 3 tabs for days 1-3 of 3-month open treatment phase (a total of 300 tablets for 100 open suvorexant patients). Total 450 Suvorexant 10 mg tablets.
 
Drug Name: Suvorexant 20 mg tablets. Amount: 4 tabs for days 4-7 of 1-week, randomized, controlled treatment phase (a total of 200 tabs for 50 double-blind suvorexant patients), then 87 tabs for days 4-90

	
of 3-month open treatment phase (a total of 8700 tablets for 100 open suvorexant patients).
 
Total 8900 Suvorexant 20 mg tablets.
 
Drug Name: Placebo tablets (to match suvorexant 10mg tablets). Amount: 3 tabs for days 1-3 of 1-week, randomized, controlled phase (a total of 150 tablets for 50 double-blind placebo patients).
 
Total 150 placebo tablets (to match suvorexant 10mg tablets).
 
Drug Name: Placebo tablets (to match suvorexant 20mg tablets). Amount: 4 tabs for days 4-7 of 1-week, randomized, controlled phase (a total of 200 tablets for 50 double-blind placebo patients).
 
Total 200 placebo tablets (to match suvorexant 20mg tablets).
 
Note: At conclusion of the study or upon drug expiration, the Merck GRS will be responsible for issuing a Drug Disposition Letter to the investigator for US based studies.
 
The investigator will be responsible for the destruction of the supplies at the study center pursuant to the ICH/GCP Guidelines, local regulations and the investigator's institutional policies. Clinical supplies will be received by [name] at the study site, handled and stored safely and properly, and kept in a secured location to which only the investigator and designated assistants have access. Clinical supplies will be dispensed in accordance with the protocol. The investigator is responsible for keeping accurate records of the clinical supplies, the amount dispensed to and returned by the patients, and the disposition at the end of the study.

2.9 Adverse Experience Reporting	
Adverse experience reporting will be conducted as outlined by the Model Study Agreement.

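### Section 2.7 compares the arms on Week-0 to Week-1 change in sTST and oTST and names no Week-0 adjustment; prespecifying one is a low-cost gain in precision

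*Combined protocol and SAP*

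**What the plan says.** The Statistical Methods part of section 2.7 gives the primary randomised analysis as "change in sTST from Controlled Week-0 to Controlled Week-1) for adjunctive suvorexant versus adjunctive placebo will be assessed using a Mixed-Effect Model Repeated Measure (MMRM"), tested at p < 0.05. The secondary randomised analysis is worded alike: "evaluation of change in oTST from Controlled Week-0 to Controlled Week-1 for adjunctive suvorexant versus adjunctive placebo, using MMRM". For neither does it list a model term: no Week-0 covariate, no shared Week-0 mean, no other covariate and no covariance structure. No other section supplies one.

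The Week-0 value exists for both outcomes. Section 2.7 lists the primary outcome as "subjective total sleep time (sTST), according to self-report, assessed at Controlled Week-0, Controlled Week-1, Open month-1, Open month-2, and Open month-3", with the same schedule for oTST. Section 2.5 places the Week-0 visit before study drug: "Controlled Week-0 (Randomization; prior to one week of double-blind, placebo-controlled adjunctive suvorexant").

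On numbers, section 2.7 states "we expect baseline mean (SD) sTST in minutes of 317 (64"), a suvorexant-placebo difference of 45 minutes, an effect size of 0.70, and 80% power "based upon a sample size of n=25 patients per group, and a two-tailed alpha of 0.05". It also states "There are no adjustments for dropout, as we expect no more than 5% dropout by the end of week 1".

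**The concern.** The label MMRM does not by itself bring in a baseline adjustment. Week-1 is the only post-baseline visit in the controlled phase. With one value per visit and complete data, an MMRM on change with treatment alone is a two-sample comparison of change. An MMRM with Week-0 in the response vector and free arm means at both visits gives the same contrast. Only a Week-0 covariate, or Week-0 means constrained equal across arms, improves precision.

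The stake is efficiency, not bias. The trial has 50 patients and no allowance for dropout, and the plan itself admits that its assumed effect is larger than in the source it cites. Information that is already collected, before dosing, should be used. Fixing the model in advance also settles which of several MMRMs of differing precision is the primary test.

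**Working it through.** **Inputs from section 2.7:** n = 25 per arm; two-tailed alpha 0.05; difference 60 − 15 = 45 min; baseline SD 64 min; dropout at most 5% by Week-1.

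**Assumptions, not in the documents:** the within-arm Week-0/Week-1 correlation r, and the Week-1 SD (s2). The 64 is stated only as a baseline SD (s1). I take s2 = 64 or 80, r = 0.3 to 0.8, and one summary value per visit.

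**The plan's own figure.** The effect size reproduces: 45/64 = 0.70. The 80% does not. A two-sided t-test with 25 per arm and effect 0.70 has 67.9% power; only a one-sided 0.05 test comes close, at 78.7%. This is a separate matter, but it shows there is no slack.

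**Variance per patient.**
- Change score: s1² + s2² − 2·r·s1·s2
- Week-0-adjusted: s2²(1 − r²)
- Difference: (s1 − r·s2)², never negative

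With equal SDs the ratio of adjusted to change variance is (1 + r)/2: 0.65, 0.75 and 0.85 at r = 0.3, 0.5 and 0.7.

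**Worked case, r = 0.5, both SDs 64.** Change SD = √(64² + 64² − 64²) = 64.0. Adjusted SD = 64·√0.75 = 55.4. Multiplying by √(2/25), the standard errors are 18.1 and 15.7 min (15.8 once the inflation below is included).

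**Power and precision.** Noncentral t, with 2n − 2 df for change and 2n − 3 df for the adjusted analysis. The adjusted variance is inflated by 1 + 1/(2n − 4) for estimating the slope. Each cell reads change → adjusted.

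| Week-1 SD | r | Power, 45 min | n per arm for 80% | 95% half-width, min |
|---|---|---|---|---|
| 64 | 0.3 | 53.9% → 71.4% | 46 → 31 | 43.1 → 35.1 |
| 64 | 0.5 | 68.3% → 79.4% | 33 → 26 | 36.4 → 31.9 |
| 64 | 0.7 | 88.2% → 92.1% | 21 → 18 | 28.2 → 26.3 |
| 64 | 0.8 | 97.1% → 98.0% | 14 → 14 | 23.0 → 22.1 |
| 80 | 0.3 | 44.0% → 52.4% | 59 → 47 | 49.0 → 43.9 |
| 80 | 0.5 | 56.6% → 60.5% | 43 → 39 | 41.7 → 39.8 |
| 80 | 0.7 | 77.1% → 77.0% | 27 → 27 | 32.8 → 32.9 |
| 80 | 0.8 | 90.1% → 89.5% | 19 → 20 | 27.3 → 27.6 |

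With 24 completers per arm and SD 64 at both visits, power is 52.2% → 69.5%, 66.4% → 77.7% and 86.8% → 91.0% at r = 0.3, 0.5 and 0.7.

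**Simulation check (20,000 trials per setting, SD 64).** Power at r = 0.3, 0.5, 0.7 and 0.8 was 53.5%, 68.0%, 88.2% and 97.1% for change, and 71.2%, 79.6%, 92.0% and 97.9% adjusted. Across both Week-1 SDs, type I error was 4.9–5.0% for change and 4.8–5.2% adjusted, so both analyses are valid.

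**The same quantity seen as imbalance.** One standard error of chance Week-0 difference is 64·√(2/25) = 18.1 min. It separates the two estimates by (1 − r·s2/s1)·18.1. For s2 = 64 that is 12.7, 9.1 and 5.4 min at r = 0.3, 0.5 and 0.7. For s2 = 80 it is 11.3, 6.8 and 2.3 min, zero at r = 0.8 and −2.3 min at r = 0.9. This restates the efficiency loss and is not a second harm.

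**The case against.** The planned comparison is not an error. It is valid, the text does not rule out adjustment, and section 2.7 is brief about every model term. The gain runs down to nil within plausible assumptions. All of that stands, and it is why the point concerns precision and not correctness.

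Other objections stand in part:
- **Nights within a visit.** sTST comes from a diary and oTST from actigraphy, and the documents do not say how nights are summarised. A model over nights is not excluded. The formulas above assume one value per visit.
- **The 45-minute effect.** The table's power figures use the plan's assumed difference. At the 18 minutes that section 2.7 reports from its cited source, with SD 64 at both visits, power goes from 13% to 17%, 16% to 20% and 24% to 27% at r = 0.3, 0.5 and 0.7. Adjustment does not rescue the design there. The interval half-widths do not depend on the effect.
- **Which SD is 64.** Section 2.7 applies 0.70 to change, so it in effect uses 64 as the change SD. On that scale, with equal visit SDs, unadjusted power is 68% throughout and adjusted power is 85%, 79%, 74% and 72% at r = 0.3, 0.5, 0.7 and 0.8. The gain remains.
- **The largest loss.** In the settings tabulated it is 0.6 point. On a wider grid (Week-1 SD 40 to 120, r 0 to 0.95) it reaches about 1.0 point, for example 66.0% to 65.0% at Week-1 SD 92 and r = 0.7.
- **Coverage.** The calculations are for covariate adjustment and were not run for the constrained-baseline model. The documents give no SD or effect for oTST, so no size can be put on that half.

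None of this favours leaving the adjustment out.

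**Conclusion.** The concern holds. Read literally, section 2.7 gives an unadjusted comparison of change for both randomised outcomes, and a Week-0-adjusted analysis is at least as efficient apart from the small cost of estimating one slope. With SD 64 at both visits, the gain in power at 45 minutes is about 17 points at r = 0.3, 11 at r = 0.5, 4 at r = 0.7 and 1 at r = 0.8. With a Week-1 SD of 80 it is 8 and 4 points at r = 0.3 and 0.5, nil at 0.7 and −0.6 point at 0.8. These figures rest on assumed r and Week-1 SD, so confidence in the size is moderate. The asymmetry is clear: a possible gain of up to about 17 points in the tabulated settings, against a loss of at most about 1. The change should be made, but the trial's validity does not depend on it.

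**What to change.** In section 2.7, before unblinding, prespecify one of these for the primary comparison:

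- (a) an MMRM of Week-0 and Week-1 sTST with the arms' Week-0 means constrained equal; or
- (b) a model of Week-1 sTST (or change) on treatment and Week-0 sTST.

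The two differ when patients drop out. Option (a) keeps the Week-0 data of patients lost before Week-1, whom the plan puts at up to 5% (0.05 × 50 = 2.5, so 2 or 3 patients); option (b) omits them. Specify the same model for oTST with Week-0 oTST.

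The cost is one sentence and at most one model degree of freedom (at most about 0.6 point of power in the tabulated settings, about 1.0 on the wider grid). No visit, assessment or data item is added.

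### The open extension judges 3-month efficacy by an uncontrolled within-patient change, and the placebo-first arm has no prespecified contrast from its last pre-suvorexant value (Week-1)

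*Combined protocol and SAP*

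**What the plan says.** Section 2.1 gives the aim of Objective 2: "To assess the subchronic (3-month) efficacy of open adjunctive (added to existing treatments) suvorexant in patients with bipolar disorder and insomnia". In Section 2.1.1, Hypotheses 3 and 4 predict that open suvorexant "despite receiving treatment as usual will yield significant increases in" subjective and objective total sleep time (sTST and oTST). Both are labelled secondary and neither names a comparator. Hypotheses 1 and 2, by contrast, are stated against placebo.

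Section 2.3 sets the treatment: "Following the 1-week randomized controlled phase, all patients will receive open suvorexant".

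Section 2.7 says of the open extension that "the key efficacy outcome will be change in sTST from Controlled Week-0 to Open Month-3, stratified by acute treatment arm". The analysis is a paired MMRM at p<0.05, and oTST gets the same contrast. Section 2.7 also lists the measurement times for the primary outcome: "subjective total sleep time (sTST), according to self-report, assessed at Controlled Week-0, Controlled Week-1, Open month-1, Open month-2, and Open month-3". The list for oTST has the same visits, and the Week-1 entry in Section 2.5 includes both measures.

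Section 2.12 plans a separate key secondary paper on the open phase. No section says what may or may not be concluded from a Month-3 change.

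**The concern.** A before-after change shows that patients slept longer at Month 3 than at Week-0. It does not show why. Both acute arms are on open suvorexant by then, so stratifying by acute arm does not supply a control.

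The plan itself offers a non-drug route to the same result. Section 2.3 admits patients "who are currently euthymic or have current syndromal or subsyndromal depressive (but not hypo/manic) symptoms", and Section 2.2 notes that "improvement in sleep quality during an acute mood episode may be an early marker of recovery from the episode". Passage of time and a lasting placebo-type response are further routes. With no limiting statement, a significant p-value on an outcome named for efficacy would meet Hypotheses 3 and 4 whichever route produced it.

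The placebo-first arm raises a second, narrower issue. Its patients take no suvorexant until after Week-1, so the change from Week-0 to Month-3 spans a week before the drug was started. The plan collects the value that separates the two periods but specifies no contrast from it.

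**Working it through.** **1. The plan's own figures.** Section 2.7 gives no expected value, sample size or power for the open-phase contrast; its stated power belongs to the randomized week and is not used here. The relevant inputs from its Power/Sample Size text are an expected sTST rise of 60 minutes on suvorexant and 15 minutes on placebo, and a baseline SD of 64 minutes. These reproduce the stated effect size: (60 − 15)/64 = 45/64 = 0.70.

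**2. Is there a control at Month 3?** Sections 2.3 and 2.7 together answer this. Everyone receives open suvorexant after Week 1, and the Month-3 test is paired within patients. There is no untreated or placebo comparison at that visit.

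**3. The placebo-first arm.** For patients with all three values, or for means estimated from one model:

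(Month-3 − Week-0) = (Week-1 − Week-0) + (Month-3 − Week-1)

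The two candidate contrasts therefore differ by exactly the placebo-week change, expected to be 15 minutes for sTST. This needs no assumption about Month 3. The plan gives no corresponding expectation for oTST. The identity holds whether or not the placebo-week gain lasts, so the Week-1 contrast cannot show how much of it persists.

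**4. Illustration: what the paired test would do with a non-drug gain.** Suppose suvorexant added nothing and only a 15-minute gain was present at Month 3. Take n = 25 per arm, SD 64 at both visits, and a within-patient correlation ρ of 0.3, 0.5 or 0.7. The persistence of the gain, the equal SD and the correlations are all assumptions. A paired t-test stands in for the MMRM.

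- SD of change = 64 × √(2(1 − ρ)) = 75.7, 64.0, 49.6 minutes.
- Noncentrality = 15/(SD of change/√25) = 0.99, 1.17, 1.51, against a critical t (24 df) of 2.064.
- Probability of a significant increase in a given arm: 16%, 20%, 31%. The nominal rate in that direction is 2.5%.
- In at least one of two independent arms, 1 − (1 − p)²: 29%, 36%, 52%. The nominal rate is 1 − 0.975² = 4.9%.

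The sizes depend on the assumptions. The direction does not: any persisting non-drug gain raises the chance of a significant increase.

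**5. Precision of a by-arm estimate.** Under the same SD and correlations, the 95% confidence half-width is t × SD of change/√n. At n = 25 this is 31, 26 and 20 minutes. If 20 patients remain (an assumption; the plan gives no Month-3 dropout figure), it is 35, 30 and 23 minutes.

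**The case against.** The strongest reply is that the plan already separates the two kinds of question. Hypotheses 3 and 4 drop the comparator, the phase is called open throughout, the hypotheses are secondary, and the test is called paired. That stands, and it makes the first part mainly a matter of labels and a missing statement of limits. It does not remove the gap: the objective and the key outcome are still framed as efficacy, with a significance threshold and no caveat.

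A reader might infer that the second paper will claim efficacy wrongly. The documents do not support that. Section 2.12 says only that the paper will describe the open continuation, not what it will conclude.

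A reader might also infer that Week-0 is the wrong baseline, or that the pre-suvorexant change would be hidden. Neither follows. Week-0 is a valid, common starting point for total change in both arms. The placebo-week change enters the randomized comparison, so a reader given both by-arm changes could subtract one from the other. What is missing is a prespecified estimate with its interval, shown beside the total.

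A third tempting reading is that a fixed share of the Month-3 gain predates the drug, for example 15/60 = 25%. That would carry a Week-1 expectation to Month 3 and assume that the placebo gain fully persists. The plan gives neither.

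Finally, MADRS and YMRS are collected at every visit (Section 2.4), so mood recovery could be examined. No such analysis is planned, and it would not replace a control.

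**Conclusion.** The point holds in two limited parts. First, the Month-3 efficacy test is an uncontrolled within-patient change, and the plan does not limit what may be concluded from it. This follows from the text alone. Second, the placebo-first arm has no prespecified contrast from its last pre-suvorexant value, although that value is collected for both outcomes. The size of this second part is the placebo-week change, expected by the plan to be 15 minutes for sTST; its share of any Month-3 total is unknown. The probabilities in the illustration rest on assumed correlations and persistence, and serve only to show that the paired test cannot tell a drug effect from another lasting gain.

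This is a change the sponsor should make, but not a flaw in the main result: the randomized Week-1 comparison is unaffected, and the open-phase hypotheses are secondary.

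**What to change.** 1. Reword Objective 2, Hypotheses 3 and 4 and the key open-phase outcome in Section 2.7 as uncontrolled within-patient change during open treatment. Report it by acute arm with 95% confidence intervals, and state that no conclusion on drug efficacy at Month 3 will be drawn. A within-patient p-value may stay if that limit stands beside it.
2. In Section 2.7, prespecify the Controlled Week-1 to Open Month-3 contrast for sTST and oTST in the placebo-first arm. Keep Week-0 to Month-3 in both arms, labelled total change, and show the two contrasts side by side in the placebo-first arm.

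Both items are needed. The second separates out the change that came before suvorexant, but it neither creates a control nor shows whether the placebo-week gain lasts.

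The cost is protocol wording and one added contrast per outcome on data already scheduled, with no new visits or patients. The downside is a weaker claim for the second paper.
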